- 3) Clinical Staff feedback: phototherapy intervention will rated using a likert scale on the following categories:

- a. Ease of use
- b. Perceived relevance to rehabilitation care
- c. Impression of effectiveness.

Post Light Therapy Outcome Assessment

Day 13: At the conclusion of the light therapy sessions (and prior to discharge from rehabilitation), a blinded Outcomes Examiner will complete the post therapy outcome assessment. This assessment will include the following:

- Symbol Digit Modalities Test
- Positive and Negative Affect Schedule (PANAS)
- Barrow Neurological Fatigue Scale

XII. Data Analysis

The primary outcome is the between-group difference (BWL vs. RL exposure) in average sleep efficiency at baseline compared to after 10 days of light treatment. ANOVA will be used to compare groups controlling for demographics, injury severity, and use of medications.

Secondary outcomes (mood, therapy participation, attention, daytime sleepiness/fatigue) between groups assessed at baseline and after 10 days of light therapy will be compared using repeated measures ANOVA. FIMTM efficiency and inpatient rehabilitation length of stay will also be compared between groups using ANOVA controlling for the same variables as the primary outcome. Descriptive analysis will summarize responses to the nursing burden questions including estimated staff time for the intervention.

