Initial scoring of the data will be done by each participating site with Actiware 5, a computer program which uses validated algorithms to determine whether an epoch of activity is “sleep” or “wake”. The Actiware 5 software calculates sleep/wake statistics based on night intervals and provides these statistics for each interval (night), as well as a mean of all intervals (nights). Using a set interval of sleep, the software scores each epoch (minute) as sleep or wake, based on a specific internal algorithm and provides analysis of data, including sleep onset latency, sleep efficiency, sleep time, wake time, % sleep, % wake, naps, resting and normal night time sleep. The Actigraphy software does not provide circadian activity rhythms analysis. The raw, de-identified actigraphy data will be transmitted in an encrypted zip file via email to the NDSC and stored on a secure server for further analyses. [name] will export edited epoch-by-epoch activity data to SAS programs to perform standard circadian activity analysis including calculation of Amplitude, Acrophase, Mesor, and the F-statistic. The activity level per epoch (minute) is used to estimate circadian activity rhythms. Circadian activity rhythms are analyzed by fitting each subject’s activity data to a 5-parameter extended cosine model.

XIII. Data Management

Table 2. Performance measures.

Performance Area	Goal	Review Schedule	Evaluation Method	Accountability*
Pre Enrollment Activities				
Manual of Procedures			Ready for IRB	[name], [name], [name]
IRB Submission			IRB approval	[name], [name], [name]
Database complete			Trial data entry	[name], [name], NDSC
Actigraphic data handling plan complete			Protocol	[name]
Research Assistant trained			Observation of test administration and scoring, physical set-up	[name], [name], [name]
Study Binders				[name]
Investigator Communication				[name], [name], [name], [name]
Post-Enrollment Activities				
Enrollment per month			Enrollment report	[name]
Completion of baseline assessments		Monthly	Review by PI, Data Report	[name], Site Coordinators
Completion of intervention		Monthly	Review by PI, Data Report	[name], Site Coordinators
Completion of outcome assessments		Quarterly	Review by PI, Data Report	[name], Site Coordinators
Data Safety Monitoring	100%	Quarterly and as needed	Review by PI, Quarterly report to Medical Monitor	[name], [name], [name]
Data audit	95% agreement	Quarterly	Rescoring and coding of 5% of assessments	[name]

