At each study site hard copy data will be stored in locked file cabinets or a secure location while the study is ongoing. When the study is complete, the data will be sent to a secure institutional records management location at each site similar to those used to store archived medical records as required by local and other regulations as applicable to each site. Washington State law requires clinical trial data be retained for 25 years. Electronic data will be entered into a database developed by the National Data and Statistical Center using an ACCESS database that will be kept behind secure firewall on servers accessible to site data managers with password-protected access. At the end of the study, each investigator will get a copy of the de-identified data. At the end of the study, all local copies of the contact information files will be destroyed.

ACG data: De-identified actigraphic data will be transmitted in an encrypted ZIP file via UW secure and government email to the NDSC and stored on a secure, password-protected server accessible only to site data managers and PIs.

Demographic, Injury Characterization, Traumatic Brain Injury Model System (TBIMS)

Outcomes: Data will be recorded on paper or directly into database developed by the National Data and Statistical Center at Craig Hospital using an ACCESS database that will be kept behind secure firewall on servers accessible to site data managers with password-protected access. Hard copies of the data will be stored in locked file cabinets or a secure location while the study is ongoing. Only de-identified data is released from the NDSC.

Paper and Pencil Tests, Cognitive Tests, Interviews: Data will be recorded on paper. All subjective questionnaires and cognitive testing scores will be entered into the secure database developed by the TBIMS NDSC at Craig Hospital using an ACCESS database that will be kept behind secure firewall on servers accessible to site data managers with password-protected access. Hard copies of the data will be stored in locked file cabinets or a secure location while the study is ongoing.

Sharing study results

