Treatment conducted as part of this study may be of benefit to an individual participant (e.g. progress on cognitive testing over time). The main sharing of study results, however, will be with the general public and medical community which may benefit from our study outcome. We plan to report our findings in published material and at medical conferences. Data sharing will follow the TBIMS protocol.

XIV. Safety and Adverse Events

Each subject will be followed medically daily by their rehabilitation resident and attending physicians and have 24 hour monitoring by rehabilitation nursing. The research assistant at each site will check in with the patient/LAR and nursing staff daily Monday through Friday to elicit any concerns. [name]. a psychiatrist in the University of Washington's Department of Rehabilitation Medicine has expertise in TBI treatment and research procedures and has agreed to be the Data Safety Monitor (DSM). He will receive a quarterly summary of all Adverse Events for review and will be contacted by the study team within 24 hours of any Serious Adverse Event to review with the study physician. Any serious adverse event will be reported to the Human Subjects Division as well immediately. At quarterly intervals after subject enrollment begins, the DSM will review and evaluate the studies' clinical efficacy and safety data. The DSM will monitor study progress, examine adverse events (AEs) and serious adverse events (SAEs), and recommend the continuation without change, suspension, or termination of a study.

XV. Definitions

Unanticipated Problems Involving Risk to Subjects or Others

Any incident, experience, or outcome that meets all of the following criteria:

- Unexpected in nature, severity, or frequency (i.e. not described in study-related documents such as the IRB-approved protocol or consent form, the investigators brochure, etc)
- Related or possibly related to participation in the research (i.e. possibly related means there is a reasonable possibility that the incident experience, or outcome may have been caused by the procedures involved in the research)
- Suggests that the research places subjects or others at greater risk of harm (including physical, psychological, economic, or social harm).

Adverse Event

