- 5) **Definitely Related:** The reaction follows a reasonable temporal sequence from administration of study treatment; that follows a known or expected response pattern to the study treatment; and that is confirmed by improvement on stopping or reducing the dosage of the study treatment, and reappearance of the reaction on repeated exposure.

Notifying the Principal Investigator

Any study-related unanticipated problem posing risk of harm to subjects or others that are not Adverse Events should be reported on the "*Unanticipated Problems Form*". Any type of serious adverse event, must be reported to the site Principal Investigator or designee within 1 business day of the event. Within the following 48 hours, the investigators must provide further information on the serious adverse event or the unanticipated problem in the form of a written narrative. This should include a copy of the completed Serious Adverse Event form, and any other diagnostic information that will assist the understanding of the event.

Notifying the Local IRB

At the University of Washington, [name] or [name] will be responsible for safety reporting to the IRB and complying with their reporting requirements. The other sites for this project will have an investigator who is responsible for safety reporting to their local IRBs. Copies of each report and documentation of IRB notification and receipt will be kept in the locked secured study file.

Notifying the Data Safety Monitor

Unanticipated problems posing risks to subjects or others and serious adverse events associated with the research will be forwarded to the Data Safety Monitor of the study at the University of Washington, within 24 hours.

Stopping Rules

There are no planned interim or futility analyses. The Data Safety Monitor may recommend stopping for safety based on overall study review.

Independent Data Safety Monitor

The Data Safety Monitor is required to review all unanticipated problems involving risk to volunteers or others, serious adverse events and all volunteer deaths associated with the protocol and provide an unbiased written report. At a minimum the Data Safety Monitor should comment on the outcomes of the event or problem and in the case of a serious adverse event or death comment on the relationship to participation in the study. The Data Safety Monitor should also indicate whether he concurs with the details of the report provided by the study investigator.

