Where there any adverse events or effects?

Yes No

Source: _____

If yes, please explain _____

Makley Sleep Log guidelines and FAQ's

Data collection

1. The sleep log can be collected by nurses or MA staff
2. Clinical staff will do data collection rounding on an hourly basis and rate the patient accordingly with a 0,1,2 or 3
3. The rating for each hour is the clinical staff's best assessment of observed sleep/non-sleep state based on how they were found, not what was being done clinically, if anything
4. Hourly ratings may be collected on paper or electronically
5. Sleep log for the first night, along with any and all information about the participant's sleep over the last 3 nights will be used to randomize. Information about the participant's sleep will be asked of any family or friends' present, clinical staff, medical chart review, and nursing notes. Please look to see if the participant has or is on any sleep medications in the past 72 hours.
6. Once the research staff has all information, they will rate the participant using the DelRS-98 item #1 to score their severity of sleep
7. Data may need to be used to reconcile actigraphy data if there are questions
8. Research staff should collect the sleep logs on a daily basis and place a copy in the participants file (de-identified)

FAQ's

1. Clinically what's the difference between 1 (falling asleep) and 2 (waking up) in the setting of night time rounds? Can we tell? **Answer:** Make your best clinically assessment. If patient is fully asleep then score = 0, if patient is fully awake then score = 3.
2. What do we do with missing hours on a sleep log? **Answer:** note it as missing data; follow-up with staff training/study education.
3. What do we do when a sleep log is entirely missing? **Answer:** keep looking to see if it can be found; include notation in case notes; follow-up with staff training/study education.

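### Does the Data Safety Monitor's quarterly review of clinical efficacy amount to unplanned interim looks at the outcome?

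*Combined protocol and SAP*

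**What the plan says.** Section XIV (Safety and Adverse Events) gives the Data Safety Monitor a quarterly task: "At quarterly intervals after subject enrollment begins, the DSM will review and evaluate the studies' clinical efficacy and safety data". The sentence after it describes the recommendation the monitor may make (continue, suspend or terminate). The material it names is study progress and adverse events, not efficacy.

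The Stopping Rules paragraph, at the end of the adverse event sections, says "There are no planned interim or futility analyses" and then "The Data Safety Monitor may recommend stopping for safety based on overall study review".

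Table 2 in Section XIII lists, for Data Safety Monitoring, "Review by PI, Quarterly report to Medical Monitor". Under Disposition of data in the same section, the de-identified actigraphy files are "stored on a secure, password-protected server accessible only to site data managers and PIs". Section XII says "Initial scoring of the data will be done by each participating site with Actiware 5", and the sleep log guidelines in the Appendix add "Data may need to be used to reconcile actigraphy data if there are questions". The one person described as blinded is the assessor on Day 13: "a blinded Outcomes Examiner will complete the post therapy outcome assessment".

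**The concern.** A monitor who evaluates efficacy every quarter sounds like someone doing interim analyses, and the plan has no alpha spending and no boundary. Section XIV also leaves open what efficacy material would be supplied, in what form, and to whom.

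Two things would be at stake. One is the error rate: if each review were a test by arm that could end the trial, the nominal 0.05 would no longer hold. The other is conduct. If results by arm were compiled each quarter and the principal investigator's review covered them, an early trend could reach sites that score the actigraphy and may use sleep logs to resolve queries about it. Actigraphy is the source of the primary outcome, sleep efficiency.

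**Working it through.** **1. The plan's own figure.** Inputs from Section VII: effect size 0.5, power 80%, 128 participants, 64 per group. Alpha is not stated; two-sided 0.05 is assumed.

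- Normal approximation: n per group = 2(1.960 + 0.842)² / 0.5² = 62.8, so 63 per group and 126 in total.
- Two-sample t-test: 63.8, so 64 per group and 128 in total. Power at 64 per group is 80.1%.
- One-sided 0.05 gives 50 per group, which does not match.

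The 128 is therefore reproduced as the size of a single fixed-sample test.

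**2. The statements on monitoring, side by side.**

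| Place | Content |
|---|---|
| XIV, quarterly review sentence | efficacy and safety |
| XIV, what the monitor receives each quarter | summary of adverse events |
| XIV, basis of the recommendation | progress, adverse events, serious adverse events |
| Stopping Rules | no interim or futility analysis; stopping for safety |
| XVIII, Protection Against Risk | quarterly adverse event summary |
| XXI, Overall Project Evaluation | quarterly safety reports (recipient's name removed) |

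Efficacy appears once. No efficacy table, measure, preparer or decision rule is attached to it. The statements are compatible: the monitor may look at the study as a whole, but acts on safety.

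**3. Effect on the final test.** Looking at data uses up type I error only if the look can lead to a claim of benefit. Here it cannot, so the error rate stays at the assumed 0.05 and the sample size stays at 128.

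**4. What the plan avoids.** Three years of recruitment (Section VII) × 4 = about 12 quarterly reviews, assuming equally spaced looks. In a simulation of 400,000 null trials, with every look tested at two-sided 0.05 and freedom to stop, the overall false positive rate was 0.207 for 12 looks (0.126 for 4, 0.231 for 16). No part of the protocol provides for such testing.

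**5. How much an early table by arm would show, if one existed.** Standard error of the standardised difference = √(2 / n per arm); half-width of the 95% interval = 1.96 × that.

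| Point | n per arm | SE | Half-width (SD) |
|---|---|---|---|
| First quarter (128/12 = 10.7 participants) | 5.33 | 0.612 | 1.20 |
| 43 participants (Table 3) | 21.5 | 0.305 | 0.60 |
| 86 participants (Table 3) | 43 | 0.216 | 0.42 |

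A t-interval would widen the first to about 1.4 SD. Against a design effect of 0.5 SD, the first two intervals are wider than the effect sought. These figures describe a hypothetical table, not an error in the trial.

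**6. The route to biased conduct.** It needs four steps: efficacy tables are prepared; they are by arm; they pass to investigators; they then alter the scoring. No statement in the protocol supports the first three. On the fourth, Section X.C has the software score sleep and wake automatically over a fixed interval from 2200 to 0600, which limits the room for discretion.

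**The case for a change.** The strongest reply is that the Stopping Rules settle when the trial may stop, but not what goes into the quarterly report or who reads it. Section XIV says the monitor will evaluate efficacy, so one team might omit efficacy and another might produce a table by arm, and both could claim to have followed the protocol. Table 2 sets the principal investigator's review beside the quarterly report, and nothing expressly withholds accumulating results by arm from investigators. A compiled comparison also tells a site more than knowing individual assignments does.

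The ambiguity is real and that part stands. It does not carry further. Review by the principal investigator also appears in the Table 2 rows for completion of assessments and of the intervention, so it reads as general oversight and is not tied to results by arm. Access to the actigraphy server exists whatever the monitor reviews, so rewording Section XIV would not alter it. Sites also randomise participants and set up the assigned light, so what a scorer may know about allocation is a separate blinding question. Finally, a monitor weighing harm may reasonably want sight of efficacy for context, and doing so creates no extra chance of claiming that bright light works.

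**Conclusion.** The concern does not call for a change. The reference to clinical efficacy in Section XIV is undefined, but read with the Stopping Rules and with the safety reports described elsewhere, it leaves one final analysis with stopping for safety only. The effect on sample size, power and type I error is nil: 128 participants, power 80.1%, alpha 0.05. The inflation to about 0.21 belongs to a testing scheme that the protocol does not contain.

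This rests on three assumptions: alpha is two-sided 0.05, which reproduces the stated 128; the monitor follows the Stopping Rules as written; and no table by arm is circulated to investigators, which the protocol neither describes nor expressly forbids. If results by arm were in fact compiled and could prompt termination or reach the sites, the matter would be more serious, but nothing in the documents says so. What is left is a gap in wording that a competent monitor and data centre would fill sensibly.

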Aim 1: In persons with TBI, prospectively compare overnight sleep efficiency in a cohort exposed to morning Bright White Light with a comparison group exposed to Red Light in an acute inpatient rehabilitation setting.

Aim 2: Explore the relationship between Bright White Light exposure during inpatient rehabilitation after TBI and mood, therapy participation, attention, rate of functional recovery and length of stay.

Aim 3: Develop and describe sleep study procedures on the inpatient rehabilitation unit for persons with TBI to support optimal and feasible design of future studies in this important area.

Research Hypothesis:

In persons with TBI, prospectively compare overnight sleep in a cohort exposed to morning Bright White Light with a comparison group exposed to Red Light in an acute inpatient rehabilitation setting.

Hypothesis 1: Individuals exposed to Bright White Light for 30 minutes each morning will have better sleep compared to the Red Light exposure group, as measured by sleep efficiency.

Hypothesis 2: Individuals with daily morning Bright White Light exposure will have better mood (as measured by the Positive and Negative Affective Schedule, PANAS), therapy participation (as measured by a 0-100 therapist rating) and attention (as measured by the Symbol Digit Modalities Test) at 10 days compared to individuals with daily Red Light exposure. The group exposed to Bright White Light will also have less daytime sleepiness and fatigue (as measured by the Karolinska Sleepiness Scale (KSS) and the Barrow Neurological Institute Fatigue Scale (BNI-FS), a faster rate of functional recovery as measured by FIM™ efficiency for the rehabilitation stay and a shorter length of stay compared to those in the Red Light group

Hypothesis 3a: Bright White Light exposure will be rated as a reasonable addition to clinical care by staff using Likert scale ratings. Categorize and quantify rates of any side effects of Bright White Light and Red Light exposure in persons with TBI during inpatient rehabilitation.

Hypothesis 3b: Bright White Light and Red Light exposure will be generally well tolerated with side effect profiles and rates similar to those observed in previous studies with other populations.

[figure not shown]
See Appendix for Flowchart on Specific Aims of this study

V. Study Description

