All adverse events occurring during the study period must be recorded. The clinical course of each event should be followed until resolution, stabilization, or until it has been determined that the study treatment or participation is not the cause. Serious adverse events that are still ongoing at the end of the study period must be followed up to determine the final outcome. Any serious adverse event that occurs after the study period and is considered to be possibly related to the study treatment or study participation should be recorded and reported immediately.

Minimum information required for each AE includes type of event, duration (start and end dates), severity, seriousness, causality to study, action taken, and outcome.

Evaluating Adverse Events

Assessment should include the intensity (severity) of the event and the relationship to Study Intervention(s).

Severity of AEs will be graded by the Investigator using the following criteria as guidelines:

- 1) **Mild:** Nuisance, barely noticeable.
- 2) **Moderate:** Uncomfortable, troublesome symptoms not significantly interfering with daily activities or sleep.
- 3) **Severe:** Symptoms significantly interfere with daily activities or sleep.

The relationship of the AE to the study treatment should be specified by the Investigator, using the following definitions:

- 1) **Not Related:** Concomitant illness, accident or event with no reasonable association with treatment.

- 2) **Unlikely:** The reaction has little or no temporal sequence from administration of the study treatment, and/or a more likely alternative etiology exists.
- 3) **Possibly Related:** The reaction follows a reasonably temporal sequence from administration of the treatment and follows a known response pattern to the suspected treatment; the reaction could have been produced by the study treatment or could have been produced by the subject's clinical state or by other modes of therapy administered to the subject.
- 4) **Probably Related:** The reaction follows a reasonable temporal sequence from administration of study treatment; is confirmed by discontinuation of the study treatment or by rechallenge; and cannot be reasonably explained by the known characteristics of the subject's clinical state.

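### The protocol defines possibly related in two conflicting ways, and the stricter definition leaves an unconfirmed new reaction without a causality grade

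*Combined protocol and SAP*

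**What the plan says.** Section XVI, under Evaluating Adverse Events, has the investigator specify the relationship of each adverse event to study treatment on five defined grades:

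- Not Related: "Concomitant illness, accident or event with no reasonable association with treatment".
- Unlikely: "little or no temporal sequence from administration of the study treatment, and/or a more likely alternative etiology exists".
- Possibly Related: "The reaction follows a reasonably temporal sequence from administration of the treatment and follows a known response pattern to the suspected treatment". The definition adds that the treatment, the patient's clinical state or another therapy could have produced the reaction.
- Probably Related: reasonable timing, a reaction that "is confirmed by discontinuation of the study treatment or by rechallenge", and no reasonable explanation by clinical state. No known pattern is asked for.
- Definitely Related: reasonable timing, a reaction "that follows a known or expected response pattern to the study treatment", improvement on stopping or reducing treatment, and reappearance on repeated exposure.

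Section XV uses the same term when it defines an unanticipated problem. One criterion is that the event be "Unexpected in nature, severity, or frequency". Another is relatedness, where "possibly related means there is a reasonable possibility that the incident experience, or outcome may have been caused by the procedures involved in the research".

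In section IV, Hypothesis 3b predicts "side effect profiles and rates similar to those observed in previous studies with other populations". The text beside it asks for rates of any side effects of either light. Section XII describes no analysis of side effects.

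**The concern.** In the section XVI scale the two conditions for Possibly Related are joined by 'and', so a known pattern is necessary. A reaction that nobody has described cannot meet that condition. Section III says that work on the use and tolerance of bright white light in this population is limited, so a reaction not seen elsewhere is something this trial should be able to register. Section XV has no such condition and treats unexpectedness as a reason to act. Two readers of the same protocol could therefore classify the same event differently.

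Three things could be affected: the grade that a new reaction receives, any duty that turns on the words possibly related, and the comparison in Hypothesis 3b if it counts only events graded as related.

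**Working it through.** No figure in the plan bears on this point, so the check is a logical one.

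**Step 1. The grades as conditions (section XVI).**

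| Grade | Timing | Known pattern | Confirmation | Other explanation |
|---|---|---|---|---|
| Not Related | – | – | – | no reasonable association with treatment |
| Unlikely | weak, and/or → | not used | not used | a likelier cause exists |
| Possibly | required | **required** | not used | may exist |
| Probably | required | **not used** | stopping or rechallenge | must be absent |
| Definitely | required | known or expected | stopping and re-exposure | not used |

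**Step 2. A new reaction.** Set timing to plausible and pattern to not known.

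- Confirmation can take 3 states: none; improvement on stopping; improvement on stopping plus recurrence on re-exposure. Recurrence is taken to presuppose improvement.
- Alternative explanation can take 3 states: none; clinical state possible but not likelier; a likelier cause.
- That gives 3 × 3 = 9 combinations.

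| Situation | Combinations | Grade that fits |
|---|---|---|
| Likelier cause exists | 3 | Unlikely |
| Confirmed, no other explanation | 2 | Probably Related |
| Unconfirmed, no likelier cause | 2 | none |
| Confirmed, clinical state possible but not likelier | 2 | none |

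The total is 3 + 2 + 2 + 2 = 9, of which 4 have no grade. Not Related is ruled out in those 4 on the reading that plausible timing without a likelier cause is a reasonable association. These are counts of logical combinations, not of events.

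**Step 3. Remove the known-pattern condition.** All 4 ungraded combinations then meet the timing condition for Possibly Related. Where a likelier cause exists, both Unlikely and Possibly could be argued. That overlap already exists for reactions with a known pattern, so the change adds no new kind of ambiguity.

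**Step 4. Which reporting duties use the grade?**

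| Duty (place) | Trigger | Depends on the scale? |
|---|---|---|
| Quarterly summary to the Data Safety Monitor (XIV; Protection Against Risk) | all adverse events, related or not | no |
| Notice to the site principal investigator, 1 business day (Notifying the Principal Investigator) | any serious event | no |
| Notice to the monitor within 24 hours, and to the IRB (XIV; Protection Against Risk) | any or all serious events | no |
| 24-hour notice (Notifying the Data Safety Monitor) | serious events associated with the research | names no grade, but narrower than the row above |
| Unanticipated problem (XV) | its own criteria | no |
| Serious event after the study period, which ends at Day 15 (XV, XVI) | considered possibly related to treatment or participation | yes, if the scale's definition is applied |

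**Step 5. Hypothesis 3b.** Two counting rules are open. If every adverse event is counted, the scale has no effect. If only events graded possibly related or higher are counted, an unconfirmed reaction not known from elsewhere drops out, which moves the profile towards the similarity that 3b predicts. The documents choose neither rule.

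**The case against.** A reader might infer that a new reaction has no grade that triggers reporting. The documents do not support this. During the study, reporting runs on seriousness and on all adverse events. Section XV carries its own broader definition and is aimed at unexpected events, and nothing says that an event must first be graded on the section XVI scale. Probably Related is also open to a new reaction once it is confirmed. A symptom that recurs at successive daily sessions could arguably be read as rechallenge, which narrows the ungraded class further.

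A reader might also infer that Hypothesis 3b confirms itself. That needs a rule counting related events only. No section contains one, and section IV speaks of any side effects.

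Third, 'known' is not defined. The list of bright-light side effects in section XVIII is open-ended, and the scale does not cite it. An event off that list is therefore not automatically barred from Possibly Related.

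All three objections stand and limit the consequences. None removes the conflict between the two definitions or the class of events without a grade. A practical residue also remains. The section under Notifying the Principal Investigator reserves the Unanticipated Problems Form for problems that are not adverse events. For a non-serious adverse event, the five-grade scale is thus the only causality assessment set out step by step. An investigator who must pick a grade may choose Unlikely, leaving the event to the quarterly summary. That is a risk about conduct, not something the text prescribes.

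**Conclusion.** The point holds in a limited form. Sections XV and XVI give one term two meanings. The stricter meaning leaves a new reaction with plausible timing, no likelier cause and no confirmation outside all five grades. The scale is also out of order, because a higher grade omits a condition that a lower grade imposes.

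The reporting exposure is mainly serious events after Day 15, and only if the scale's meaning of possibly related is applied there; that duty also covers relation to study participation, which is broader than the scale. The possible downgrading of non-serious new reactions comes second. The effect on Hypothesis 3b is conditional on a counting rule that is not stated. The number of events affected cannot be derived from the documents. The wording should be corrected, but it does not undermine safety reporting as a whole.

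**What to change.** Reconcile sections XV and XVI. In the definition of Possibly Related, delete the clause that requires a known response pattern and use section XV's reasonable-possibility wording for that grade, so that the term means the same throughout, including for serious events after the study period.

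For Hypothesis 3b, add to section XII a table of all adverse events by arm regardless of causality grade, with the related subset as a second table. The comparison with earlier studies then does not rest on the grading alone.

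The cost is a wording change and one extra table. The downside is that a few more events will be graded possibly related and will need review.
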